5.10 Clinical Criteria for Early Trial Termination

Early trial termination will be the result of the criteria specified below:

1. Quality or quantity of data recording is inaccurate or incomplete
2. Poor adherence to protocol and regulatory requirements
3. Incidence or severity of adverse drug reaction in this or other studies indicates a potential health hazard to subjects
4. Plans to modify or discontinue the development of the study drug
5. An early stopping rule will be put into place such that if at any time during enrollment of the first 10 patients considered initially resectable at screening, if 3 or more of these patients have local progression on the study treatment and are then deemed locally unresectable the trial will close early.

In the event of Merck decision to no longer supply study drug, ample notification will be provided so that appropriate adjustments to subject treatment can be made.

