7.0 STATISTICAL ANALYSIS PLAN

7.1 Statistical Analysis Plan Summary

The primary objective of this phase II study is to determine the overall response rate in patients with squamous cell carcinoma of the head and neck who have residual disease following definitive radiation with or without systemic therapy. This will be a single arm study of 24 patients with Stage I-IVB HNSCC who have residual disease after being treated with definitive radiation with or without systemic therapy.

The expected rate of resolution of disease without any further therapy is thought to be approximately 10%. This is derived from the Princess Margaret Hospital experience of 493 patients undergoing definitive chemoradiation for head and neck SCC, approximately 50% had less than a complete response to chemoradiation therapy at 8-12 week post therapy assessment²⁶. An additional 33% achieved CR between weeks 12 and 24. Of patients taken to neck dissection with less than a complete response (CR) the rate of positive residual tumor cells within the neck was 35%. This is substantially higher than the rate of positive residual cells at neck dissection in patients who achieve a CR to initial therapy, which was 9%. Thus it is estimated, that approximately 10% of patients that would likely have had pathologic residual disease at the 8-12 week assessment will achieve pathologic CR by 24 weeks without any further intervention. This estimate is given by:

the percentage of patients achieving a CR between weeks 12 and 24 x (the rate of pathologic positivity in non CR patients – the rate of pathologic positivity in CR patients)

$$= 33\% \times (35\% - 9\%) = 8.7\%, \text{ or approximately } 10\%.$$

Thus, assuming a baseline response rate of 10% (based on the Princess Margaret experience discussed above) and an improvement in response rate to 27% after treatment of chemoradiation, we will have 81% power to detect this difference with 24 patients by exact one-sample binomial test at one-sided significance level of 0.10. If 27% or more of patients in the study develop a partial or complete response to pembrolizumab, this strategy will be deemed worth of further investigation.

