9.2 Quality Management System

9.2.1 Safety Monitoring

The Yale Cancer Center Data and Safety Monitoring Committee (DSMC) will provide the primary oversight of data and safety monitoring. The Yale DSMC will review and monitor compliance, toxicity and deviations from this study. The committee is composed of clinical specialists with experience in oncology and who have no direct relationship with the study. Information that raises any questions about participant safety will be addressed with the Principal Investigator.

The DSMC will review this protocol at a minimum of once every six months. Information to be provided to the committee includes: a study narrative by the PI, a summary DSMC report produced by OnCore (which includes participant accrual, response, trial status history, SAEs, Adverse Events, Deviations and survival); audit results, and monitoring reports as applicable. Other information (e.g. scans, laboratory values) will be provided upon request.

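### The plan has no response-based futility rule; an optional, non-binding look at the first 12 patients would keep power at about 81%

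*Combined protocol and SAP*

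**What the plan says.** **Design.** Section 7.1: "This will be a single arm study of 24 patients with Stage I-IVB HNSCC". The null response rate is 10% and the alternative 27%, and the section states that "we will have 81% power to detect this difference with 24 patients by exact one-sample binomial test at one-sided significance level of 0.10". The section plans no interim analysis of response. It also calls the strategy worth pursuing if the observed response rate reaches 27%. It does not state the number of responders at which the test rejects.

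**Stopping.** Section 5.10 has one numeric criterion: "An early stopping rule will be put into place such that if at any time during enrollment of the first 10 patients considered initially resectable" three or more progress locally on treatment and are then judged unresectable, the trial closes. Section 5.3 gives a similar rule without the condition of local progression. The other criteria in 5.10 cover data quality, adherence, adverse reactions and the drug's development. None concerns lack of activity.

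**Oversight.** Under 9.2.1 the DSMC reviews the trial at least every six months, with a report covering "participant accrual, response, trial status history, SAEs, Adverse Events, Deviations and survival". No response threshold is attached.

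**Patient pathway.** Response is read at progression or after four cycles, whichever is earlier (3.1); four cycles take 12 weeks (2.1). Under 2.1, initially resectable patients who progress after two cycles stop the drug and go to surgery. Section 5.3 also stops study therapy for progression before four cycles.

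**The concern.** The resectability rule measures harm from delay. It does not ask whether there is any benefit to set against that delay. It counts no responses and leaves out patients who are unresectable at entry, so it can stay silent while nobody responds.

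Resectable patients without progression wait about 12 weeks before surgical re-evaluation. The background (4.2.1) stresses finding poor responders early, because few patients who recur can have curative-intent salvage surgery. If the drug adds nothing, the plan gives no statistical reason to stop enrolling further patients into that wait. The DSMC would see the low count but would have no agreed point at which to act.

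**Working it through.** **Inputs.** From 7.1: n = 24, p0 = 0.10, p1 = 0.27, one-sided exact binomial test at 0.10, stated power 81%. From 1.0: enrolment over an estimated 18 months. From 2.1 and 3.1: response read by 12 weeks. From 5.2.1.2: up to 6 weeks of dosing interruption after cycle 4 for required assessments. Assumptions: even accrual, and a look when the first 12 treated patients have been assessed. The plan specifies no look.

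**1. The plan's own figure.** With X ~ Bin(24, p):
- P(X ≥ 4 | 0.10) = 0.214, which exceeds 0.10.
- P(X ≥ 5 | 0.10) = 0.0851, so the test rejects at 5 or more.
- P(X ≥ 5 | 0.27) = 0.8170.

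The stated 81% is reproduced, but only with the unwritten cut-off of 5 of 24.

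**2. Can the existing rule stay silent?** Its chance of firing is P(Bin(10, q) ≥ 3), where q is the chance of becoming unresectable. The documents give no q. Over an assumed range:

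| q | 5% | 10% | 20% | 30% |
|---|---|---|---|---|
| Rule fires | 1.2% | 7.0% | 32.2% | 61.7% |

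**3. Add the look: advise a stop at 0 of 12.** The chance of a stop is (1 − p)^12:
- p = 0.05: 0.540
- p = 0.10: 0.282
- p = 0.27: 0.023

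If the advice is always followed, the chance of final success is Σ over x ≥ 1 of P(Bin(12, p) = x) × P(Bin(12, p) ≥ 5 − x):
- p = 0.27: 0.8124, a loss of 0.8170 − 0.8124 = 0.0046.
- p = 0.10: 0.0839.

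If the advice may be overruled, the type I error to quote is the single-stage 0.0851. A futility look cannot raise it.

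**4. What the look gives up.** After 0 of 12, success needs 5 or more of the remaining 12. That chance is 0.202 at 27% and 0.004 at 10%.

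**5. The look has to be chosen with care.** Power at 27%, final cut-off 5 of 24:

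| Stop if | Power |
|---|---|
| 0 of 8 | 78.1% |
| 0 of 10 | 80.3% |
| 0 of 12 | 81.2% |
| at most 1 of 12 | 77.0% |
| at most 1 of 16 | 81.1% |

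Earlier or stricter looks fall below the stated 81%.

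**6. Patients spared.** Accrual is 24/18 = 1.33 a month, so the 12th patient enrols at month 9.
- Read-out at 12 weeks (2.76 months): month 11.8, with 11.76 × 1.33 = 15.7 enrolled and 8.3 spared.
- With all 6 further weeks used (18 weeks, 4.14 months): month 13.1, with 17.5 enrolled and 6.5 spared.
- Average at a true rate of 10%: 0.282 × 8.3 = 2.3, or 0.282 × 6.5 = 1.8.

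**7. The other success criterion.** 27% of 24 is 6.48, so an observed rate of 27% or more means 7 or more responders. P(X ≥ 7 | 0.27) = 0.482, and 0.481 with the look. The 81% does not belong to that criterion.

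**The case against.** A single-stage exact design with 24 patients is legitimate and its power is correctly stated. Choosing not to plan a futility look is a matter of judgement. That stands.

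The plan also targets the main harm directly. The resectability rule can close the trial, and patients who progress have their own exit. A reader might infer that every resectable patient is held from surgery for 12 weeks whatever happens. Sections 2.1 and 5.3 do not support that: the full wait applies to those without progression. (Section 2.1 describes the cycle-2 scan both as routine and as done when clinically indicated. That needs reconciling, but it is a separate matter.) A reader might also infer that nobody sees response data before the end. Section 9.2.1 shows that the DSMC does; what is missing is a rule.

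The yield is modest. At the plan's own 10% rate the look lets the trial continue 72% of the time and spares about 2 patients on average. Some of these would be unresectable at entry, and the documents do not give the split. The figure of 8 applies only when the rule fires and read-out is prompt. Stopping would also reduce the PD-L1, immune adverse event, survival and biomarker data, which are already thin at 24.

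These points limit the weight of the concern. They do not remove it: the individual exits do not stop further enrolment, and the resectability rule does not count responses.

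**Conclusion.** The gap is real: no rule in the documents acts on a low response count, and a trial with no responses could enrol all 24. A non-binding look at 0 of 12 costs about 0.5 points of power (81.7% to 81.2%) and leaves type I error at 8.5%; the 8.4% figure applies only if the stop is always obeyed. It would advise a stop 28% of the time at a true rate of 10% and 54% at 5%.

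The power figures rest on a final cut-off of 5 of 24, which the plan does not write down. The saving rests on even accrual over the estimated 18 months and on read-out 12 to 18 weeks after the 12th enrolment.

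A reader might go further and conclude that the design is invalid or that the 81% is wrong. Neither follows: the 81% reproduces under the stated test. This is an optional improvement of moderate yield.

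**What to change.** First reconcile the two success criteria in 7.1, the exact test (5 or more of 24) and the observed rate of 27% or more (7 or more of 24, power about 48%), and write the chosen cut-off down. The 81% should be restated only if it is 5 of 24.

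Then add to 5.10 and 7.1, for example: *When the first 12 treated patients have had their primary response assessment, the DSMC will consider closing accrual if none has responded. This guidance is non-binding and accrual is not paused.*

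With the 5 of 24 cut-off, state the operating characteristics: power 81.2% if the advice is followed and 81.7% without the look; type I error 8.5%; chance of advising a stop 54%, 28% and 2.3% at true rates of 5%, 10% and 27%.

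The cost is a short amendment and one extra DSMC table, about 0.5 points of power, a 2.3% chance of wrongly advising a stop at a true rate of 27%, and fewer secondary and biomarker data if the trial closes early.

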PD-L1 expression in human HNSCC tissue samples is reported in 46.4-100% of cases, although the definition of staining necessary to be considered positive varies from study to study. Ranges of PD-L1 expression are 49.2-70% in HPV (+) tumors and 29-40% in HPV (-) tumors, with a trend towards increased expression in HPV (+) tumors¹⁸. That targeting this pathway is of clinical benefit was demonstrated in a phase 1B study of pembrolizumab, an anti-PD-1 antibody. In patients with recurrent or metastatic HNSCC, pembrolizumab demonstrated a 20% response rate in heavily pretreated patients¹⁷. Depending on the level of PD-L1 expression chosen as a cutoff, however, the response rate could be as high as 45.5%.

Given that the response to anti PD-1 therapy appears related to levels of PD-L1 expression, and the fact that PD-L1 is inducible, the potential impact of radiation therapy on PD-L1 expression is of considerable interest. A study of TUBO tumors treated with 12 Gy of radiation and examined three days later demonstrated an increase in expression of PD-L1 on dendritic cells and tumor cells, compared with controls¹⁹. This is in keeping with other well-documented effects of radiation on the immune system. Radiation leads to enhanced T-cell infiltration in the tumor microenvironment, promotes T-cell cytokine production and cytotoxicity, and increases the expression of tumor antigens, thereby improving tumor cell antigenicity²⁰.

Also enticing is the potential for a synergistic effect between immunotherapy and radiation. In a preclinical mouse glioma cell line, the combination of radiation therapy and PD-L1 blockade led to a near doubling of survival in comparison to either a PD-L1 alone arm, or a radiation alone arm²¹. In addition, the combined treatment group demonstrated an increase in CD8 effector T-cells (CD8/IFN- γ /TNF- α) and a decreased number of regulatory T-cells (Tregs, CD4/FOXP3+) compared to controls. Moreover, to test for long-term immunity, untreated, and “cured” mice were challenged with flank injection of GL261-luc tumor cells. All naïve mice developed tumors by 21 days after injection, whereas none of the “cure” mice developed tumors within 60 days of implantation, suggesting this approach leads to prolonged protective T-cell immunity.

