5.3 Treatment Allocation

Patients with Stage I-IVB HNSCC of the larynx, hypopharynx, oropharynx, nasopharynx, or oral cavity) who have been treated with curative intent radiation, chemoradiation, or cetuximab and radiation within 6-24 weeks and have biopsy proven residual disease will be eligible for enrollment.

All patients upon biopsy confirmation of residual disease will have restaging scans (CT neck/chest/abdomen/pelvis). Patients will require evaluation by an ENT to determine whether their disease is considered resectable or unresectable. Patients will then receive pembrolizumab at a dose of 200mg Q3 weeks for 4 cycles. A CT scan of the neck/chest/abdomen/pelvis will be performed at the end of cycle 2 to check for progression of disease (irPD), defined using immune related response criteria. Patients with progression prior to four cycles of pembrolizumab will discontinue study therapy.

After four cycles patients will undergo repeat CT neck/chest/abdomen/pelvis and a biopsy. Patients will then be re-evaluated by otolaryngology to determine the current status of their local/locoregional disease and to determine whether it is technically resectable. At this time patients that are deemed resectable can go on to surgical resection, and those deemed unresectable or who refuse resection can continue on pembrolizumab until evidence of progression or for up to 1 year. These patients will not be evaluable for the study endpoints, although their response rates and overall survival will be reported. An early stopping rule exists, such that during enrollment of the first 10 patients considered resectable, at screening if 3 or more become unresectable during the study the trial will close. The plan is to enroll 24 patients.

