5.9 Subject Replacement Strategy

Patients will be replaced if they do not receive at least one cycle of pembrolizumab.

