The primary endpoint of this trial will be overall response rate and the secondary endpoint will be progression-free survival. We will use descriptive statistics to calculate frequency and proportion for the response rate to pembrolizumab. 95% confidence interval will also be provided. Exact binomial test will be used to compare the observed response rate versus historical control. For the secondary endpoint, we will use Kaplan-Meier estimator to present the progression-free survival.

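### Section 7.1 gives two unreconciled success criteria: the exact test passes at 5 of 24 responders (power 82%), but the written 27% rule needs 7 of 24 (power 48%)

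*Combined protocol and SAP*

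**What the plan says.** Section 7.1 (Statistical Analysis Plan Summary) describes a single-arm trial of 24 patients with an assumed baseline response rate of 10% and a target of 27%. On that basis it states: "we will have 81% power to detect this difference with 24 patients by exact one-sample binomial test at one-sided significance level of 0.10". The sentence that follows gives the decision rule: "If 27% or more of patients in the study develop a partial or complete response to pembrolizumab, this strategy will be deemed worth" further investigation. The last paragraph of 7.1 returns to the test: "Exact binomial test will be used to compare the observed response rate versus historical control".

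No responder cut-off is printed for the test. Nothing says whether the test or the 27% sentence decides, or whether both must be met. Section 4.2.3.1 also links 27% to further investigation, but its wording concerns the rate to which response might be raised, which reads as a true target rate.

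Two other places bear on the denominator. Section 5.3 says of some patients: "These patients will not be evaluable for the study endpoints". Section 5.9 says: "Patients will be replaced if they do not receive at least one cycle of pembrolizumab".

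**The concern.** The 27% appears in two roles. In the power statement it is the assumed true response rate under the alternative. In the next sentence it is a cut-off for the proportion observed in the study. A trial with about 80% power at a true rate of 27% must have a critical value well below 27%. If the observed rate must itself reach 27%, power at a true rate of 27% will be near one half.

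The go/no-go call in this uncontrolled, open-label trial rests on the primary response rate. If the 27% sentence is the decision, its power is far below the 81% that readers are given. If the test is the decision, the 27% sentence is wrong. If 27% is a deliberate second hurdle, the plan does not report the power of the decision it will make. In every case 5 or 6 responders has no agreed interpretation, and the criterion could be chosen after the result is known.

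**Working it through.** **Inputs, all from section 7.1:** n = 24; null rate 0.10; alternative 0.27; exact one-sample binomial test; one-sided level 0.10; stated power 81%; go rule of an observed CR + PR proportion of at least 27%. X is the number of responders, X ~ Binomial(24, p).

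**Step 1: reproduce the plan's figure.** The critical value is the smallest r with P(X ≥ r | 0.10) ≤ 0.10.
- P(X ≥ 4 | 0.10) = 0.2143, too large.
- P(X ≥ 5 | 0.10) = 0.0851, acceptable.

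The test therefore rejects at 5 or more of 24 (5/24 = 20.8%). Power is P(X ≥ 5 | 0.27) = 0.8170, which matches the stated 81%. A normal approximation would give 84.4%, so the exact test is the one behind the plan's figure.

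**Step 2: the written go rule.** 0.27 × 24 = 6.48. Six responders give 6/24 = 25.0%, which falls short. Seven give 7/24 = 29.2%, so 7 or more are needed.
- Type I error: P(X ≥ 7 | 0.10) = 0.0075.
- Power: P(X ≥ 7 | 0.27) = 0.4820.
- The true rate at which this rule reaches 80% power is about 35.4% (78.9% at 35%, 81.8% at 36%).

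**Step 3: how often the two disagree.** They differ when X is 5 or 6. At p = 0.27 this probability is 0.8170 − 0.4820 = 0.3350.

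For illustration, section 4.2.1 reports of recurrent or metastatic disease that "pembrolizumab demonstrated a 20% response rate in heavily pretreated patients". At p = 0.20, P(X ≥ 5) = 0.5401 and P(X ≥ 7) = 0.1889. That is a different population, and the finding does not depend on it.

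**Step 4: sensitivity to the denominator.** The figures above assume that all 24 patients count. The documents give no number of evaluable patients, so 20 to 24 is an assumed range.

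| Evaluable n | Test cut-off | Test power at 27% | 27% rule cut-off | 27% rule power at 27% | P(disagree) at 27% |
|---|---|---|---|---|---|
| 24 | 5 | 0.817 | 7 | 0.482 | 0.335 |
| 23 | 5 | 0.785 | 7 | 0.432 | 0.353 |
| 22 | 5 | 0.748 | 6 | 0.569 | 0.179 |
| 21 | 5 | 0.708 | 6 | 0.518 | 0.190 |
| 20 | 5 | 0.662 | 6 | 0.464 | 0.198 |

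The 27% rule is stricter than the test at every n in this range.

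**The case against.** The strongest reply is that the two sentences need not conflict. A trial can reject 10% and still miss a higher bar set for further development, and 7.1 never says that a significant test means go. On that reading the plan has one go rule, and the fault is only that its power is not reported. The stricter bar could even be reasoned: if the promised 95% interval is an exact Clopper-Pearson interval (the plan does not name the type), its lower limit is 7.1% at 5/24, 9.8% at 6/24 and 12.6% at 7/24, so only 7 or more excludes 10%.

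This has force against assuming that the 27% sentence is a slip, and the fix leaves that choice to the sponsor. It does not remove the problem. The plan gives neither this rationale nor the relation between test and bar, and the power printed immediately before the go rule is not the power of that rule.

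A second reply is that 27% means the true rate throughout. That suits 4.2.3.1. It does not suit 7.1, where the condition concerns the share of patients in the study who respond.

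A third is that section 5.3 is weak evidence for a smaller denominator. The excluded patients are most naturally those who continue treatment after cycle 4, while sections 3.1 and 6.2.2.12.2 settle response by the end of four cycles. That is fair: 5.3 is unclear, and no passage supports 20 as a floor. The denominator range is illustrative, and the 5-versus-7 discrepancy does not rest on it.

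Finally, the estimate and its interval will be reported whatever the rule, and safety is unaffected. That is true, but the success criterion for the primary endpoint is still undefined for a likely set of results.

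**Conclusion.** The concern holds. The 81% power is correct for the exact test, which succeeds at 5 or more of 24. It is not the power of the go rule in the next sentence, which needs 7 or more of 24 and has 48.2% power at the design alternative. Under the written rule, a drug performing exactly as hypothesised is slightly more likely to fail than to pass. The two criteria give opposite answers about one time in three (33.5%) when the true rate is 27%.

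These figures assume exact binomial calculation, all 24 patients in the denominator, and a literal reading of the 27% sentence as an observed proportion. The 5-of-24 cut-off is derived from the stated test and is not printed in the plan. This must be fixed, because it concerns the primary success criterion and the power attached to it.

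**What to change.** In 7.1, replace the 27% sentence with one success rule stated as a responder count, with its own operating characteristics. The sponsor should choose one:

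- **Option A.** Worth further investigation if at least 5 of 24 patients have a CR or PR (type I error 0.085; power 82% at a true rate of 27%). This matches the test and the stated power.
- **Option B.** If a stricter observed-rate bar is intended, at least 7 of 24, with the go decision reported as type I error 0.0075 and power 48% at a true rate of 27%, and a sentence saying that it applies in addition to the exact test.

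Under either option, state who is in the denominator and give the matching count if fewer than 24 are evaluable. With 22 evaluable, for example, the test needs 5 or more and the 27% rule 6 or more. Section 4.2.3.1 can stay as it is, since it reads as the true target rate.

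The cost is one sentence and no extra patients. Option A lowers the written bar from 7 responders to 5. Because the trial is open-label, that change should be dated and should say whether response data had been seen. Option B means accepting and reporting 48% power for the go decision.
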